COMIRB Protocol
COLORADO MULTIPLE INSTITUTIONAL REVIEW BOARD
[name] [contact] [contact]

PROTOCOL #: 13-2639

(Use Protocol Manager on the COMIRB Website)

Version Date: December 9, 2016

Project Title: Improved behavioral outcome in allogeneic hematopoietic stem cell transplant patients by reducing caregiver distress: Behavioral and physiological evidence

Principal Investigator: [name]

**Co-Investigators: [name]
[name]
[name]**

**[name]
[name]
[name]**

I. Hypotheses and Specific Aims:

Patients receiving an allogeneic hematopoietic stem cell transplant (HSCT) undergo a demanding conditioning protocol. In contrast to cancer treatments using standard-dose chemotherapy, radiation, and/or surgery, treatment protocols for HSCT are more intense and life threatening. Following transplantation, patients are at increased risk for graft versus host disease (GvHD). To ensure adequate support, monitoring and safety, allogeneic HSCT patients are required to have a caregiver available 24/7 for at least the first 100 days following transplantation and occasionally longer if complications arise. Allogeneic caregivers assist with a complicated medical procedure with 70% patient survival. The patient's quality of life (QOL) is dependent on the quality of care provided by their caregiver. Caregiver distress impacts the quality of care they provide and thus patient QOL.

We showed that a behavioral intervention for caregivers of allogeneic HSCT patients reduced caregiver distress. *A gap remains with regard to evaluating intervention impact on patient QOL.* During the first 100 days, patients may be poor targets for behavioral intervention due to significant fatigue and debilitation. Carry over to patients as improved care may derive from caregivers participating in supportive programs. Patient and caregiver dyads will be randomized to either treatment as usual (TAU) or "fone" PsychoEducation and Relaxation (fPER) which provides a combination of face to face sessions and Smartphone video chat when a caregiver is unable access the clinic to meet with an interventionist. fPER caregivers will receive a biofeedback device for stress management. 225 dyads will be randomized from 2 sites (private and university based) and followed for 6 mo. following transplantation. Specific aims are:

Hypotheses:

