Primary hypotheses: Patients whose caregivers receive fPER will have improvements in FACT-BMT compared to TAU.

Secondary hypotheses: Caregivers who receive fPER will have reduced distress compared to TAU.

Specific Aims:

Aim 1: Create a *Community Advisory Board* (CAB) consisting of allogeneic HSCT patients, caregivers, blood cancer oncologists, support staff and study investigators to provide input.

Aim 2: Assess *patient QOL* following an allogeneic HSCT using the FACT-BMT as the primary patient outcome. Patients whose caregivers receive fPER will have improved QOL compared to caregivers assigned to TAU.

Aim 3: Test the impact of fPER on a *caregiver composite distress score* (encompasses depression, anxiety, and stress) as the primary caregiver outcome. Caregivers receiving fPER will have reduced distress.

Aim 4: Assess *biomarkers* of allostatic load in patients prior to transplant and caregivers during the transplant process using novel biomarkers (hair cortisol and telomeres). **fPER** will be associated with reduced allostatic load in caregivers compared to TAU. Patient hair cortisol collected only before transplant will relate to QOL at intake.

Deliverables include 1) developing evidence supporting *improved patient QOL* associated with 2) *minimizing caregiver distress* as well as 3) *a manualized intervention, fPER*, based on stakeholder input and oversight available for dissemination.

II. Background and Significance:

A.1. Impact of the Condition on the Health of Individuals and Populations (Criterion 1)

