Allogeneic hematopoietic stem cell transplant (HSCT) caregivers must be available 24/7 for the first 100 days and often longer following a transplant. However behaviorally and more importantly medically healthy caregivers are essential for the best patient outcome. Few interventions for caregivers have been tested by randomized clinical trials (RCT). Our objective is to determine if a stress management intervention for allogeneic HSCT caregivers compared to self-care relying on resources of the transplant program (treatment as usual, TAU) would be associated with lower stress. We designed a randomized control trial with intent-to-treat of an eight session manualized stress management intervention provided to caregivers following transplant. Subjective behavioral data collected longitudinally for 12 months using standardized instruments was entered blindly. The HSCT caregivers were recruited from a community transplant program between November 2008 and April 2012. The study included a consecutively approached sample of 267 caregivers of allogeneic HSCT patients. 148 (mean age=53.5 years, 75.7% female) were randomized to a manualized intervention (n=74) or TAU (n=74). 101 caregivers reached the three month follow-up with drop outs associated with patient and/or caregiver factors. The intervention included an eight session stress management program provided to caregivers by a social worker during the immediate post-transplant period that focused on learning about stress, changing role(s) of the caregiver, cognitive behavioral approach to managing stress, paced respiration with a commercial biofeedback device, and identifying resources. A panel of questionnaires and physiological markers was collected from the caregivers five times over the course of one year beginning in the peri-transplant period. The primary outcome measure was self-reported perceived stress. Secondary outcome measures included depression, anxiety, caregiver burden, physical health, sleep, trauma and composite scores of these measures. Groups did not differ at baseline. Controlling for age, the intervention resulted in significantly lower ($p=0.039$) caregiver perceived stress (primary outcome) at 3 months post-transplant (Mean=20.0, SD=1.0) compared to TAU (Mean=23.0, SD=1.0) with an effect size (ES) of 0.39. The intervention group showed significantly better ($p=0.019$) scores on a secondary composite score that includes depression, anxiety, and other distress measures (Mean=-0.22, SD=0.13) compared to TAU (Mean=0.23, SD=0.13) with an ES of 0.45. This study had limitations due to problems with low minority subject recruitment, logistics of collecting dependent measures when patients and caregivers moved out of the area, as well as missing data. While needing further study within more settings, this approach is likely to improve caregiver well-being and potentially that of patients.

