Figure 4. Study timeline common to CBOI (n=150) and UCH(n=75) sites with randomization by permuted block design for caregivers. Patients (indicated by +P) will provide a hair sample *only* at baseline and no blood samples beyond routine clinical assessments but they will complete questionnaire in tandem with caregivers. **Key to Sampling**

At each phase, patients and caregivers will complete the same battery of questionnaires that includes the Center for Epidemiological Studies-Depression scale (CES-D), the perceived stress scale (PSS), Pittsburgh Sleep Quality Inventory (PSQI), and the State-Trait Anxiety Inventory (STAI). Additionally the patient will complete the FACT-BMT each time while the caregiver completes the Caregiver Reaction Assessment (CRA). Both the patient and the caregiver will additionally complete a demographic questionnaire that includes questions regard age, diagnosis, income, and other standard questions regarding nutrition, health behaviors, and health services utilization. At study completion, an exit questionnaire will address each subject’s evaluation of the study and the group in which they were assigned. Each subject will be assigned a code number for de-identifying purposes at consenting and this number will be the only identifier on questionnaires. The confidential code sheet that identifies the subject’s randomized treatment group based on a permuted block design, subject name, and contact information will be kept in a locked cabinet as well as in a password protected secure data base. After the randomization table is created by the biostatistician, this will be available only to Drs. [name] and [name].

Intervention groups
TAU. All patients and caregivers, regardless of randomization, are informed of what to expect during the transplant process and how to locate available support resources within each program. Patients and caregivers

are given information that is specific to their involvement in the transplantation process and recovery phase. Subjects randomized to TAU will be encouraged to participate in available support programs at their respective centers which are very similar between sites and include individual counseling as well as support groups. Due to the impact of our prior intervention on caregiver distress, we will provide each caregiver randomized to TAU a workbook prepared for someone to use without one-on-one sessions with a therapist.

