Data Aggregation, Distributional Assumptions, Missing Data/Attrition. Data will be screened for errors and outliers. Appropriate transformations will be made for non-normal outcomes. The pattern of participant dropout will be examined to ensure a reasonably equal distribution of participants lost to follow-up between groups. The analytic approach proposed uses maximum likelihood techniques that can include participants with incomplete data without need for imputation. These techniques are robust under certain conditions such that group comparisons will not be biased as long as missing data is ignorable.^{132,133} If this is not sufficient to minimize influences of particular observations, a sensitivity analysis will be conducted to help determine effects of missing data. Separate analyses of only those participants who complete the study will be conducted.

Verification of Randomization and Inclusion of Covariates. Preliminary analyses will validate that there are no baseline differences between intervention groups. We expect baseline differences will be accounted for by randomization, but should differences remain we will co-vary variables that are both correlated with the outcome and that differ by group.

Analytic Strategy In general, outcomes will be analyzed with linear mixed models comparing intervention (**fPER**, TAU) in patients and caregivers separately. An alpha level of 0.05 will be used to evaluate significance of the a priori planned comparisons. Two-tailed tests are proposed in order to detect differences between **fPER** and TAU in either direction. The software SAS PROC MIXED will be used.¹³⁴ The analytic aims and hypotheses are briefly stated, followed by overall analytic plan for primary and secondary outcomes:

Aim 2: Assess patient QOL following an allogeneic HSCT by the FACT-BMT as the primary patient outcome. Patients whose caregivers receive fPER will have improvements in FACT-BMT compared to TAU.

Aim 3: Test impact of fPER on caregiver composite distress score of depression, anxiety, and stress as the primary caregiver outcome. Caregivers who receive fPER will have reduced distress compared to TAU.

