For hypotheses addressing group differences for patients and separately for caregivers, outcomes will be evaluated with the same design: 2 groups (**fPER**, TAU) at 2 clinics (CBCI, UCH) over 4 times (prior to transplant, 6 wks., 3 mo., 6 mo.). Mixed models will specify group, clinic, time, and their interactions as fixed effects and subject as a random effect, where subject is assumed independently normally distributed with mean 0 and variance independent of the random errors. The primary caregiver model of composite distress will include caregiver age as a covariate because it related to caregiver distress in our prior study¹¹; secondarily, we will investigate inclusion of patient FACT-BMT as a covariate. The primary patient model of FACT-BMT will include no covariates, but secondarily will explore inclusion of caregiver distress as a covariate.

Aim 4: Assess biomarkers of allostatic load in patients prior to transplant and caregivers during the transplant process using novel biomarkers. Patient's hair cortisol will predict their QOL and distress at the beginning of the transplant process. fPER will be associated with reduced allostatic load in caregivers who receive fPER compared to those receiving TAU.

Linear mixed models will similarly be used to evaluate group differences in these biomarkers separately in patients and caregivers. Caregiver age and patient FACT-BMT will be evaluated for inclusion in caregiver models. Caregiver composite distress score will be evaluated for inclusion as a covariate in patient models.

Subject sample size and power analysis. Our prior trial demonstrated medium effect sizes (0.39-0.45) for PEPRR in caregivers. We believe the proposed modifications in **fPER** will likely increase its effect for caregivers. However, the effect of **fPER** on

Table 2. Minimum detectable effect sizes with specified sample size and power

Sample Size Per Group	80% Power	85% Power	90% Power	95% Power
112 Dyads	0.19	0.20	0.22	0.24
74 Dyads	0.23	0.25	0.27	0.30
62 Dyads	0.25	0.27	0.29	0.32

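### Both primary models include group-by-clinic terms but the plan does not say how the two clinic effects are combined; default equal weighting would cost 12.5% in variance under the plan's own assumptions

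*Combined protocol and SAP*

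**What the plan says.** Section IV.F gives one design for the FACT-BMT and caregiver-distress models: two groups, two clinics, four times. "Mixed models will specify group, clinic, time, and their interactions as fixed effects", with subject as a random effect having a single variance. The caregiver model adds caregiver age; the patient model has no covariates.

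On testing, the Analytic Strategy says "An alpha level of 0.05 will be used to evaluate significance of the a priori planned comparisons" and "The software SAS PROC MIXED will be used". It names no LS-means margins, contrast weights or test type, and has no rule for dropping a null interaction.

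The enrolment table in IV.B plans 37 TAU and 38 fPER dyads at UCH, and 75 and 75 at CBCI. The Figure 4 caption agrees: "Study timeline common to CBOI (n=150) and UCH(n=75) sites". (IV.B and IV.C swap the Site 1 and Site 2 labels, but names and sizes match.)

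The primary hypothesis in Section I is "Patients whose caregivers receive fPER will have improvements in FACT-BMT compared to TAU". The secondary hypothesis makes the same comparison for caregiver distress. Neither these nor Aims 2 and 3 concern a difference in effect between clinics.

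**The concern.** Once group-by-clinic terms are in the model, there is no single fPER-TAU effect until someone chooses how to average the two clinic effects. The PROC MIXED defaults average them equally, so the clinic with one third of the dyads gets half the weight. That is less precise than weighting by size.

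The power section claims only 80-85% power for FACT-BMT and calls 112 dyads per group necessary for it, so there is little slack. The power table appears to have been computed without a clinic factor, so it makes no allowance for equal weighting. Leaving the weights open also means that the primary contrast could be settled after the data are seen.

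**Working it through.** **1. The plan's own figure.** The power table in IV.F ("Table 2. Minimum detectable effect sizes with specified sample size and power") is reproduced by a plain two-group formula on a half-d scale: (z for two-sided 0.05 + z for power) × √(2/n) / 2. For n = 112:
- 80%: (1.960 + 0.842) × √(2/112) / 2 = 0.187 (printed 0.19)
- 85%: 0.200 (printed 0.20)
- 90%: 0.217 (printed 0.22)
- 95%: 0.241 (printed 0.24)

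The 74- and 62-dyad rows match as well. No clinic term enters.

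**2. One visit, unit SD, equal variance and retention.** Variance of the within-clinic difference:
- UCH: vU = 1/37 + 1/38 = 0.05334
- CBCI: vC = 2/75 = 0.02667

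Variance of the combined contrast:
- Weights 1/2, 1/2: 0.25 × (vU + vC) = 0.02000
- Weights 1/3, 2/3: vU/9 + 4vC/9 = 0.01778
- Ignoring clinic: 1/112 + 1/113 = 0.01778

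Ratio = 0.02000/0.01778 = 1.125. Standard error × √1.125 = 1.061. Equivalent sample: 225/1.125 = 200 dyads.

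**3. Power and detectable effect.** New power = Φ((1.960 + z_power)/√1.125 − 1.960):
- from 80%: Φ(0.681) = 0.752
- from 85%: Φ(0.865) = 0.806

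On the table's scale, with arms of 112 and 113, the 80% entry is 2.802 × √0.01778 / 2 = 0.187; with equal weighting it is 2.802 × √0.02000 / 2 = 0.198.

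**4. The planned four-visit model.** I computed exact generalised least squares for the group × clinic × time random-intercept model. Retention was 100%, 80%, 66% and 55%. The last two figures are the plan's 34% and 45% losses; the 80% at 6 weeks is assumed. Within-subject correlation was assumed to be 0.3, 0.5 or 0.7. The equal-weight to reduced-model variance ratio was 1.125 for the 3-month, 6-month, change-from-baseline and all-visit-average contrasts at every correlation. At correlation 0.5 the 6-month variances are 0.03108 and 0.02762. The full model with weights 1/3 and 2/3 reproduces the reduced model's variance.

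**5. Unequal retention (assumed; the documents give none by clinic).** Take a 15-point gap at each follow-up visit, with overall retention held at 80/66/55%. The 6-month ratio at correlation 0.5 in the four-visit model is:
- UCH 90/76/65%, CBCI 75/61/50%: 1.06
- UCH 70/56/45%, CBCI 85/71/60%: 1.23

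**6. Unequal outcome variance (also assumed).** With CBCI/UCH variance ratio r, the step 2 ratio becomes 0.25(vU + r·vC)/(vU/9 + 4r·vC/9):

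| r | 0.7 | 1 | 1.25 | 1.43 | 2 |
|---|---|---|---|---|---|
| ratio | 1.27 | 1.125 | 1.04 | 1.00 | 0.90 |

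Break-even: r = vU(1/4 − 1/9)/(vC(4/9 − 1/4)) = 1.43, an SD about 20% higher at CBCI.

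**The case against.** The strongest reply is that the plan never commits to default tests or LS-means. A planned contrast with suitable weights fits inside the stated model and carries no penalty. This stands: what the documents show is an unspecified weighting. A reader might infer that the trial as planned loses 12.5% in variance or falls to 75% power. The documents do not support that, because the loss depends on a default the plan does not name, and the power section gives no FACT-BMT effect size. The power figures are relative to nominal power only.

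Second, an equal average over a private and a university site is a legitimate target, and it does not shift with accrual or dropout. That is true, but no section states that target or sizes the trial for it. The prior trial cannot settle the matter: "The HSCT caregivers were recruited from a community transplant program between November 2008 and April 2012", a single program. That is a good reason to look at clinic-specific effects, but it does not choose the weights for the primary test.

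Third, the direction could reverse if CBCI outcomes were much more variable. Step 6 concedes this. Under the plan's own model, which has one subject variance, the reduced fit is never the less precise.

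Fourth, the shift in the detectable effect is small (0.187 to 0.198), and the gap can be closed without deleting terms. Both points stand and are reflected below.

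**Conclusion.** The point holds as a minor one. The primary fPER-TAU contrast is not fully defined, because both primary models contain group-by-clinic terms and no clinic weights are given.

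If default equal weighting is used, with common variance and equal retention, the contrast's variance is 12.5% higher than the same data allow. With the assumed 15-point retention gap, the excess at 6 months is about 6% to 23%. The result rests on the planned 75/150 split being achieved.

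No bias or Type I error inflation follows, and none should be inferred. Equal weighting is a valid but less efficient choice here, and it targets a different average only if the effect differs by clinic.

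**What to change.** For both primary outcomes, add one of the following to IV.F:

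- Test fPER against TAU in a model with group, clinic, time, group-by-time and clinic-by-time (plus caregiver age in the caregiver model, as planned); or
- Keep the full model and pre-specify a contrast weighted 1/3 (UCH) and 2/3 (CBCI) as the primary test.

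Under equal retention the two are equivalent. With unequal dropout, the first weights clinics by retained information and the second keeps the planned sizes. In either case, report the group-by-clinic terms and the clinic-specific effects with intervals as a pre-specified secondary heterogeneity check.

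The cost is a sentence or two, with no change to data collection or sample size. The downside is that, if effects differ by clinic, the estimate leans toward CBCI relative to an equal average by (2/3 − 1/2) = 1/6 of the clinic difference; for example, 0.3/6 = 0.05 SD if the clinics differ by 0.3 SD. The precision gain disappears if CBCI outcome variance exceeds about 1.43 times that of UCH.

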In the initial RCT, the primary outcome measure was the PSS and a number of secondary outcomes were further collected including measures of depression, anxiety, sleep, and overall health.¹⁴ We extracted the first principal component from four secondary measures and PSS by principal component analysis (PCA) to produce a composite distress score¹⁴ which was significantly affected by the PEPRR intervention as shown in Figure 5. In the present study we have reduced overall subject burden by eliminating questionnaires with replicative questions so the first principal component will be extracted from 3 (rather than 5) outcomes that had the highest loading for caregivers in the PCA of our previous study (stress, depression, and anxiety measures described below). This composite distress score will be the *primary outcome for the caregiver* in our conceptual model as shown in Figure 3. The main focus for patients is their quality of life so the *primary outcome measure for patients* will be the Functional Assessment of Cancer Treatment – Blood/Marrow Transplant (FACT-BMT).⁸ We will collect the same stress, depression, and anxiety measures (specified below) in patients for secondary analyses as collected in caregivers.

Figure 5. Age-adjusted means (+SEM) for PEPRR (n=74) and TAU (n=74) groups based on a mixed model analyses for (Panel A) primary outcome PSS and (Panel B) secondary composite distress measure. On both outcomes, PEPRR was significantly less stressed at 3 months relative to TAU (p < 0.03; ES=0.39-0.45). Note that groups were not different at baseline on either outcome. Average time relative to transplant at which the intervention began was 16+10 days.

Demographic survey. At recruitment each subject will complete a comprehensive demographic survey to establish basic facts regarding SES, age, sex, education level, relationship to the patient, caregiving hours, and employment status.

Hormone Status. At recruitment, only female subjects will complete a survey regarding their current hormone/menopausal status.

General Health Questions. This will query health habits (e.g., exercise, nutrition, physician visits) and specific medication use. At each follow up phase we will ask each caregiver *as well as patients* about changes in medication use or the presence of an individual psychotherapist or similar support groups.

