Perceived Stress Scale (PSS). Stress will be assessed with the PSS¹⁰⁰ which measures the degree to which situations are perceived as stressful. Items on the PSS measure the degree to which the subjects feel their lives are unpredictable, uncontrollable and overwhelming on a 5 point Likert scale. It has been validated in 2,387 respondents across demographic characteristics (i.e. age, sex, SES, race)¹⁰¹ with superior psychometric properties (reliability alpha of 0.84). We found PSS to be elevated above controls in caregivers of HSCT patients as well as other caregivers of patients in phase 1 trials as indicated in Figure 6. The PSS was the primary outcome measure in the initial RCT and was significantly lower than TAU at 3 mo. post-transplant as indicated in Fig. 5. *The effect size (ES) for this difference was .39.*

Center for Epidemiological Studies – depression scale (CES-D). Subjects will complete the CES-D,¹⁰² a measure developed for the general population and with a long history of use in caregiver research.¹⁰³⁻¹⁰⁵ The 20 item scale includes reference to sleep disruption, appetite disturbance, overall fatigue, and depressed affect. Scores range from 0-60 with scores over 16 viewed as reflecting significant depressive symptomatology. Test-

retest validity ranges from .51 to .67 over 2-8 weeks with an internal validity of .85 for a normal population.¹⁰² The ES for the difference in CES-D between TAU and PEPRR was 0.46.

Spielberger State-Trait Anxiety Inventory (STAI). High anxiety been related to caregiver burden and stress.¹⁰⁶ Subject anxiety will be assessed using the State/Trait Anxiety Inventory (STAI).¹⁰⁷ The STAI is a 40 item scale on which the subjects will indicate how they feel “right now” (state) on a 4 point Likert scale. Internal consistency is .89 to .91. The ES for the difference in STAI between TAU and PEPRR was 0.66.

Pittsburgh Sleep Quality Index (PSQI). The PSQI provides information regarding sleep latency, sleep efficiency and sleep duration. The PSQI is a 26 item scale on which the subjects will rate seven domains of sleep on a 4 point Likert scale. The PSQI is a widely used questionnaire¹³⁶ that provides acceptable reliability and validity with diagnostic sensitivity of 89.6% and specificity of 86.5%.^{137, 138}

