FACT-BMT (Patient only). Patient Quality of Life (QOL) follows a time course after allogeneic HSCT⁹ which is characterized by deterioration during hospitalization and as much as one year post-transplant in allogeneic HSCT.¹⁰⁸ Patients experiencing the greatest improvement in the first year continue to show higher QOL over subsequent years¹⁰⁹ with female sex being a significant negative contributor to QOL in the patient.¹⁰⁸ Thus the primary outcome measure for HSCT patient QOL is the FACT-BMT⁸ which has excellent reliability (.86), validity (.89) and sensitivity to change.

Caregiver Reaction Assessment (Caregiver only). We will include a highly recommended²⁸ measure of caregiver burden, the Caregiver Reaction Assessment (CRA).¹¹⁰ The 24 item CRA is scored on a 5 point Likert scale with subscales of esteem, family support, finances, schedule, and health. It has excellent test-retest reliability of .9 and responsiveness to change of .81. We noted that while distress decreased in the PEPRR group, the CRA remained similar across groups indicating that the intervention mitigates caregiver distress in spite of constant burden. This measure remains as exploratory only.

Carer Support Needs Assessment Tool (Caregiver only). We have included an assessment called Carer Support Needs Assessment Tool (CSNAT).¹³⁵ The instrument is comprehensive in obtaining carers’ perspectives of key aspects of support needed during their time as a caregiver for an allogeneic hematopoietic stem cell transplant (HSCT).

Caregiver Intervention Feedback (fPER Caregiver only). We have included an assessment called Caregiver Intervention Feedback. We ask very specifically about each component of the intervention. The questionnaire allows caregivers to provide feedback about the intervention earlier than the current 6 month Exit Questionnaire. The idea with this addition is that we would provide a forum for participants to comment on the intervention in their own words.

Exit Questionnaire. Each subject will complete the Exit questionnaire at the end of study. The aim of this questionnaire is to get feedback from subjects on our designed intervention program and see what changes should be made based of their input. Also for those subjects in the fPER program, we want to get feedback on the emWave2_device verses the entrainment and learned behavior of slowed breathing. This feedback advice from subjects will be used in future clinical studies and clinical application.

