patient QOL is indirect, and thus smaller effect sizes would be expected. We estimated minimum effect sizes detectable for different power specifications for a recruited sample size of 112 per treatment group and also for smaller sample sizes, allowing for increased variability due to estimated losses to follow-up of 34% at 3 mo., and 45% at 6 mo. based on our prior caregiver trial. Estimates are conservative since **fPER** has been specifically modified to reduce attrition. 112 dyads (consisting of a caregiver and patient) randomized to each group provide excellent power (>95%) for detecting the medium effect size expected for the composite distress score in caregivers and are necessary to provide adequate power (80-85%) for detecting smaller effect sizes expected for the FACT-BMT QOL measure in patients. Estimates are also conservative because mixed model analyses that include all subjects (even those with only a single observation) have been shown to provide the greatest power.¹²⁷

G. Summarize Knowledge to be Gained:

This study will provide empirical evidence regarding both behavioral and possible physiological efficacy of a stress management psychoeducation program for caregivers and the impact on patient QOL. This is one of the few studies of its kind that promises to provide not only information regarding behavioral outcome for the patients as far as quality of life but also impact their caregivers. The results of this study will lead to the availability of a manual developed for this intervention that can be disseminated to other HSCT programs leading to improved patient QOL and reduced caregiver distress.

H. References:

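### A subject effect alone, with conventional errors, imposes one variance and one correlation on four uneven visits; single-visit and change tests could miss 5% either way, and an unstructured covariance is a cheap safeguard

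*Combined protocol and SAP*

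**What the plan says.** Section IV.F, Analytic Strategy, sets one design for patients (FACT-BMT) and, separately, caregivers (composite distress): two groups, two clinics, and visits before transplant and at 6 weeks, 3 months and 6 months. "Mixed models will specify group, clinic, time, and their interactions as fixed effects and subject as a random effect", and "subject is assumed independently normally distributed with mean 0 and variance independent of the random errors". The software is PROC MIXED with a two-sided 0.05 level for planned comparisons. Those comparisons are not listed by visit or contrast. No error covariance, random slope, robust variance or degrees-of-freedom method is given.

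On missing data the same section relies on maximum likelihood without imputation: "These techniques are robust under certain conditions such that group comparisons will not be biased as long as missing data is ignorable". It adds completer analyses and a conditional sensitivity analysis, both about missing data. The power paragraph allows for "estimated losses to follow-up of 34% at 3 mo., and 45% at 6 mo. based on our prior caregiver trial".

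Section IV.E (Potential Scientific Problems) says something different: the last valid measure is carried forward, and dropout is taken as completely at random unless there is reason to think otherwise.

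**The concern.** A subject intercept plus independent, equal-variance errors has two covariance parameters. It forces the same variance at all four visits, and the same correlation between 6 weeks and 3 months as between pre-transplant and 6 months. The visits are unevenly spaced and a transplant falls after the first, so neither equality can be taken for granted.

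If either fails, model-based standard errors for contrasts that single out a visit are wrong. The direction depends on the contrast and the variance pattern, so it cannot be predicted in advance. The ignorable-dropout protection claimed for the likelihood analysis also needs a correct covariance when dropout depends on observed scores. The planned missing-data sensitivity analyses do not examine this.

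**Working it through.** **Inputs from the documents.** Visits coded 0, 1.5, 3 and 6 months; 112 per group; loss of 34% at 3 months and 45% at 6 months; two-sided 0.05.

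**Assumed inputs.** Loss at 6 weeks of 17%, and all SDs and correlations. The main scenario splits the variance into equal thirds: stable, decaying at 0.8-0.9 per month, and noise. The correlation over a gap of g months is then 1/3 + (1/3)r^g. Over 6 weeks this is 0.57-0.62. The only anchor is the CES-D figure: "retest validity ranges from .51 to .67 over 2-8 weeks with an internal validity of .85 for a normal population".

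**The plan's own figure.** For "Table 2. Minimum detectable effect sizes with specified sample size and power", use d = (1.96 + z_power)·sqrt(2/n). With n = 112 and 80% power, d = 2.80 × sqrt(2/112) = 0.374, and half of that is 0.187, printed as 0.19. All 12 cells reproduce as d/2 (Cohen's f). The 62 row corresponds to 45% loss (112 × 0.55 = 61.6) and gives d = 0.50, the yardstick for bias below. This reproduction says nothing about the covariance.

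**Type I error.** 2·(1 − Φ(1.96/ratio)), where ratio = true SE / model SE.

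**Equal SDs, complete data, r = 0.8.** The six pairwise correlations are 0.572 (twice), 0.504 (twice), 0.455 and 0.421. The fitted common correlation tends to their mean, 0.505.
- 6-month change: ratio² = (1 − 0.421)/(1 − 0.505) = 1.169, so 7.0%.
- 6-week change: ratio² = (1 − 0.572)/(1 − 0.505) = 0.864, so 3.5%.
- Group difference at any one visit: ratio 1, so 5.0%.

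**Unequal SDs, complete data.** The fitted variance tends to the mean of the four variances.
- SDs 1/1.2/1.2/1: mean 1.22. At 3 months ratio² = 1.44/1.22, so 7.1%.
- SDs 1.3/1.2/1.1/1: mean 1.335. At 6 months ratio² = 1/1.335, so 2.4%.
- SDs 1/1/1/1.3: mean 1.1725. At 6 months ratio² = 1.69/1.1725, so 10.3%.

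**Both decay rates, complete data / loss of 17/34/45%:**

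| SDs by visit | 3-month difference | 6-month difference |
|---|---|---|
| equal | 5.0% / 5.0% | 5.0% / 5.5-5.6% |
| 1/1.2/1.2/1 | 7.1% / 7.2% | 3.0% / 3.5-3.6% |
| 1.3/1.2/1.1/1 | 4.0% / 3.4-3.5% | 2.4% / 2.5-2.6% |
| 1/1.1/1.2/1.3 | 5.9% / 6.5-6.6% | 8.2% / 9.6% |
| 1/1/1/1.3 | 3.4% / 3.7% | 10.3% / 11.7-11.8% |

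The 6-month change is 6.7-7.0% / 6.8-7.1% with equal SDs, about 4.5% when SDs peak mid-course, and 7.1-7.3% / 5.8-6.0% when they fall. The group main effect is 5.0% with complete data and 4.1-6.0% with loss. The 3-df group-by-time test is 5.1-5.6% and 4.5-6.9%. Constant correlation with equal SDs gives 5.0% throughout.

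**Finite-sample check.** 112 versus 113 subjects, the same loss, clinic ignored, 4,000 trials per scenario. Over the 3-month difference, 6-month difference and 6-month change, REML compound symmetry rejected at 2.3-11.6%. The unstructured fit rejected at 4.2-5.6%, using t degrees of freedom (subjects seen at the visit minus 2) as a stand-in for Kenward-Roger. Monte Carlo SE is about 0.35 points at 5%.

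**Bias.** With completely random dropout there is none, whatever the covariance. With no true effect and dropout tied to the last score in TAU only (odds ratio 1.6-2.7 per SD lower), the fitted 6-month difference (fPER minus TAU, in 6-month SDs) shifts by:
- +0.01 to +0.03 with equal SDs;
- +0.02 to +0.05 with a mid-course peak;
- +0.05 to +0.09 with falling SDs;
- −0.01 to −0.04 with rising SDs.

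Against 0.50, a shift of 0.03 is 6%. The unstructured fit stays within 0.005 of zero.

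**The case against.** The plan never says its errors are independent with equal variance; that is inferred. Nothing in the documents shows compound symmetry failing. The account of QOL as "characterized by deterioration during hospitalization and as much as one year post-transplant" is a mean course in patients and says nothing about spread. The CES-D retest range is compatible with constant correlation and is not the patient primary outcome. The only visit-specific test tied to the documents is the prior trial's: "On both outcomes, PEPRR was significantly less stressed at 3 months relative to TAU". With equal SDs, that 3-month difference sits at 5.0%. The group-by-time test that the model naturally yields also stays near nominal. If values are carried forward as section IV.E says, the loss columns do not describe the analysed data. If dropout is completely random, the bias disappears; the bias scenario was built with one-sided, outcome-dependent dropout.

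All of that stands, and it keeps the point modest. It does not remove it. The plan names no primary contrast, so the more robust tests cannot be assumed to be the ones used. The 3-month difference does move once SDs vary by visit. If another error structure was intended, it still has to be stated.

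A reader might infer that the primary test is inflated, perhaps to double digits. The documents do not support that: the direction is unknown. The double-digit figures need either an SD that jumps at 6 months or pure decay, with 6-week correlations of 0.72-0.85, above the CES-D range.

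**Conclusion.** The point holds as a cheap improvement of modest severity. As written, and with conventional errors, the model rests every visit-specific test on an assumption that the documents neither support nor contradict. If it fails, the 0.05 level is not secured for such tests, and an overly conservative test with lost power is as possible as a liberal one. How far this touches the primary analysis cannot be settled until the primary visit or contrast is named. Bias is a secondary matter: it arises only under outcome-dependent dropout and is small at equal SDs in the main scenario. Confidence is medium, because every SD and correlation and the 6-week loss are assumed.

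**What to change.** In Analytic Strategy, replace the random intercept with an unstructured within-subject covariance over the four visits (PROC MIXED, REPEATED with TYPE=UN) and Kenward-Roger degrees of freedom. Fix the fallback order for non-convergence: heterogeneous Toeplitz, then compound symmetry with robust standard errors. Name the primary visit or contrast for each primary outcome in the same sentence.

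Reconcile section IV.E (last value carried forward) with section IV.F (maximum likelihood without imputation), since the covariance change applies to the likelihood analysis.

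The cost is a few sentences and ten covariance parameters instead of two, which 225 subjects per model should support. If compound symmetry is in fact true, the unstructured fit loses roughly 0.6-1.5 points of power for a 0.4 SD difference. In a run of 8,000 trials with constant correlation 0.5, power went from 66.7% to 65.8% at 6 months and from 72.1% to 71.5% at 3 months.
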